### 3.7 Safety Assessment

Safety data will be analyzed based on the Safety Population for both Phase 1b and Phase 2a and summarized by pooled treatment and pooled placebo: Phase 1b (uncomplicated SAB) vs Phase 1b placebo, and Phase 2a (complicated SAB) vs Phase 2a placebo.

Safety data will be summarized by actual treatment received based on the Safety Population.

#### 3.7.1 Adverse Events

AEs will be captured from the date of informed consent through EOS.

All AEs will be coded to system organ class (SOC) and preferred term (PT) using MedDRA. The Investigator will grade all AEs using the National Cancer Institute Common Terminology Criteria for Adverse Events (NCI CTCAE) v5.0.

TEAEs are defined as AEs occurring after the first dose of study drug through TOC for study drug (Day 12) or through EOS for SAEs.

An overview of AEs will be provided including counts and percentages of subjects with the following:

- Any AEs
- Any TEAEs
- Any study drug related TEAEs
- Any BAT related TEAEs
- Any SAEs
- NCI CTCAE grade 3/4/5 AEs
- NCI CTCAE grade 3/4/5 TEAEs
- Any TEAEs leading to interruption of study drug

- Any TEAEs leading to withdrawal of study drug
- Any TEAEs leading to discontinuation of study
- Any AEs leading to death

Counts and percentages of subjects will also be presented by SOC and PT for each of the categories in the overview. Chi-square test p-value will be provided to compare AP-SA02 and placebo.

Listings will be presented specifically for SAEs and TEAEs leading to discontinuation of study drug based on randomized subjects.

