The planned enrollment in each of the Phase 1b cohorts is 4 subjects per cohort (AP-SA02 to placebo 3:1); however, this may be modified after DRC review. Subjects in Phase 1b Cohort 1 will receive IV bolus infusion doses of blinded study drug every 6 hours for 5 study days (a total of 20 doses) in an inpatient location in addition to BAT. Following 5 days of dosing with study drug, additional study visits will be conducted at the End of Treatment (EOT) for study drug (Day 5), at the Test of Cure (TOC) for study drug (Day 12), TOC for BAT (7 days \pm 1 day] after the end of BAT), and at End of Study (EOS) (28 days after the end of BAT). Subsequent cohorts (eg, planned Phase 1b Cohort 2 or additional cohorts [up to 3]) will proceed similarly; however, the duration of dosing may be modified after the DRC review of the preceding cohort.

Figure 2 shows the study schema.

Figure 2. Study Schema

Note: EOT for IV BAT is dependent on the duration of the Investigator prespecified antibiotic therapy (14 days [uncomplicated SAB] or 28 days [complicated SAB] to 56 days).

1. The screening period will be up to 3 days.

BAT = best available therapy; D/d = day; EOS = End of Study; EOT = End of Treatment; hrs = hours; IV = intravenous(ly); q6h = every 6 hours; SAB = *Staphylococcus aureus* bacteremia; Scr = Screening.

In Phase 2a, approximately 42 subjects will receive IV bolus infusion doses of blinded study drug every 6 hours, for no more than 14 days as determined by analysis during or after Phase 1b, in addition to BAT. Following 5 days of dosing with study drug, additional study visits will be conducted at EOT for study drug (Day 5), TOC for study drug (Day 12), TOC for BAT (7 days \pm 1 day] after the end of BAT), and EOS (28 days after the end of BAT). If the study drug EOT is extended after the DRC review, the study drug TOC visit will occur 7 days after the last day of dosing and the study drug EOS visit will occur 28 days after the end of BAT.

The following dose cohorts are planned:

Phase 1b

- Cohort 1 (AP-SA02 to placebo 3:1):
 - Planned approximately 2×10^9 PFU (1×10^9 PFU/phage) administered via IV bolus infusion every 6 hours for a period of 5 days;

- Cohort 2 (AP-SA02 to placebo 3:1):
 - Planned approximately 2×10^{10} PFU (1×10^{10} PFU/phage) administered via IV bolus infusion every 6 hours for a period of 5 days; and

Note: The dose, frequency, and duration may be modified after DRC review. Maximum dosing duration will be no more than 14 days.

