4.3.2 Criteria for Ad Hoc Data Review Committee Review of Study

In the event that any of the following criteria are encountered, the DRC may, as described in the DRC Charter, convene to review available data and make recommendations, including but not limited to, if the cohort should stop or pause the study, enrollment, or treatment and/or make recommendations to modify the protocol (ie, decrease or change the dose of study drug, modify safety monitoring):

Phase 1b criteria

- If any unacceptable toxicity (as determined by the Investigator or Sponsor's Medical Monitor) occurs;
- If ≥ 1 serious AE (SAE) considered attributable to AP-SA02 (confirmed by unblinding) occurs; or
- If ≥ 2 of all treated subjects experience similar SAEs or Grade 3 (CTCAE version 5.0) AEs meeting the following criteria:
 - Onset between start of dosing and 7 days after last dose; and
 - Considered attributable to AP-SA02 (confirmed by unblinding).

Note: All \geq Grade 3 (CTCAE version 5.0) laboratory abnormalities should be confirmed with a repeat test within 24 hours.

Phase 2a criteria

- If ≥ 1 serious AE (SAE) considered at least possibly attributable to AP-SA02 (confirmed by unblinding) occurs; or
- If ≥ 2 of all treated subjects experience the same or similar adverse events that are Grade 3 or higher meeting the following criteria:
 - Onset between start of dosing and 28 days after last dose; and
 - Considered attributable to AP-SA02 (confirmed by unblinding).

Note: All \geq Grade 3 (CTCAE version 5.0) laboratory abnormalities should be confirmed with a repeat test within 24 hours.

Further enrollment of subjects and dosing of the investigational product should be halted until a safety review of the event is completed. If the DRC recommends, and the Sponsor then implements, stopping study treatment and, subsequently, the Sponsor, independent of or following a DRC recommendation, proposes to restart the study, a substantial amendment will be submitted to regulatory agencies, Institutional Review Board (IRB)/Independent Ethics Committee (IEC), and Office of Human Research Oversight (OHRO). The study will not restart until the amendment has been approved by regulatory agencies and IRB/IECs. These requirements are not applicable if the Sponsor pre-emptively pauses study treatment for subject safety pending DRC review and the DRC recommends resuming study treatments and/or any study modifications recommended do not represent substantial protocol changes.

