- TEAEs, which are defined as AEs occurring after the first dose of study drug through TOC for study drug (Day 12) or through EOS for SAEs;
- Proportion of subjects with acute kidney injury (AKI), defined as stage 1 or higher using modified Risk-Injury-Failure-Loss-End-stage renal disease (RIFLE) criteria ([Appendix D](#)) at any time within the first 7 days or new need for renal replacement therapy between Day 1 and EOS;
- Vital signs;
- Clinical laboratory evaluations;
- Change in CRP from baseline to EOS;
- Change in IL-10 from baseline through TOC for study drug (Day 12);
- Change in SA isolate sensitivity to AP-SA02 between initiation of study drug and the last isolation of SA from a sterile site (blood, joint fluid, tissue);
- Change in SA isolate susceptibilities to anti-staphylococcal antibiotics from baseline;
- Change in SA isolate susceptibility to BAT from baseline; and
- Clinical and microbiological outcomes by foci of infection.

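### In Phase 2a, non-serious study-drug-related AEs starting after Day 12 can meet the protocol's 28-day review criterion, yet no summary table identifies them as drug-related

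*SAP*

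**What the plan says.** SAP 3.7.1 defines the window: "TEAEs are defined as AEs occurring after the first dose of study drug through TOC for study drug (Day 12", extended to EOS for SAEs. Protocol 7.2 has the same definition for Phase 2a ("defined as AEs occurring after the first dose of study drug through TOC for study drug (Day 12) or through EOS for SAEs"), and it recurs in Protocol 7.1 and SAP 2.3.1 and 2.3.2. The two documents agree on what a TEAE is. Collection is wider than this window: "AEs will be captured from the date of informed consent through EOS" (SAP 3.7.1).

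Protocol 4.3.2 lists the criteria on which the DRC may convene ad hoc. One Phase 2a criterion is met when at least two treated subjects "experience the same or similar adverse events that are Grade 3 or higher meeting the following criteria". Those criteria are "Onset between start of dosing and 28 days after last dose" and attribution to AP-SA02, confirmed by unblinding. The event need not be serious; SAEs have a separate criterion. The Phase 1b counterpart stops at 7 days after last dose.

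The SAP 3.7.1 overview has one row on relatedness to study drug, and it is restricted to TEAEs. The rows not restricted to TEAEs (all AEs, all SAEs, all Grade 3 to 5 AEs, AEs leading to death) are not split by relatedness. The SOC/PT tables repeat the overview categories, with a chi-square comparison of the arms. SAP 3.1.3 says that all data will be listed by subject.

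If dosing is extended, "the study drug TOC visit will occur 7 days after the last day of dosing" (Protocol 3.1; SAP 2.2.1 repeats it).

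**The concern.** For Phase 2a the protocol treats an attributable severe event as relevant to a safety review for four weeks after the last dose. The SAP reports drug-related events for one week after it, unless they are serious. An event can therefore count towards a DRC review, for which Protocol 4.3.2 says enrollment and dosing should be halted, and still be absent from the one table a reader would consult for drug-related events.

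This is a first-in-human trial, and Protocol 1.3.2.1 records that no adverse drug reactions have yet been identified. Safety and tolerability are part of the Phase 2a objective. The drug-related table will be a main source for the product's first human safety profile. As written, it leaves out part of a period that the trial's own criterion covers. SAP section 6, which lists changes from the protocol's analyses, does not mention the difference.

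**Working it through.** **Inputs**
- Last planned dosing day: Day 5 (Protocol section 3 and Table 1).
- TOC for study drug: Day 12, or 7 days after the last dosing day if dosing is extended (Protocol 3.1, SAP 2.2.1). Appendix A allows ±1 day if the subject has been discharged.
- Onset limit for the review criterion: last dose + 28 days in Phase 2a, + 7 days in Phase 1b (Protocol 4.3.2).
- Maximum dosing duration: 14 days (Protocol 3.1).
- EOS: 28 days after the end of BAT; Days 39 to 81 in Appendix A.

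**The plan's own figure.** TOC = 5 + 7 = Day 12, which reproduces the stated day.

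**Phase 1b.** The criterion closes on 5 + 7 = Day 12, the day the TEAE window closes. The gap is 0.

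**Phase 2a, 5-day dosing.** The criterion closes on 5 + 28 = Day 33. The gap is 33 − 12 = 21 days (Days 13 to 33), and 21/33 = 64% of the criterion's days. With TOC on Day 11 or Day 13 the gap is 22 or 20 days.

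**Phase 2a, 14-day dosing.** TOC = 14 + 7 = Day 21 and the criterion closes on 14 + 28 = Day 42. The gap is again 42 − 21 = 21 days (21/42 = 50%).

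**Where a related, non-serious Grade 3 event with onset on Day 20 would appear (Phase 2a, 5-day dosing)**

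| Output | Included? | Identified as drug-related? |
|---|---|---|
| Study-drug-related TEAEs, overview and SOC/PT | No | – |
| All TEAEs; Grade 3 to 5 TEAEs | No | – |
| All AEs; Grade 3 to 5 AEs | Yes | No, and pre-dose events are included |
| Subject listings | Yes | Not a summary by arm |

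**Are the data there?** Phase 2a requires at least 28 days of BAT, counting days before randomization. If k of those days precede Day 1, the earliest EOS is 28 − k + 28 = 56 − k. With k = 3 (an assumption based on the 72-hour limit on prior antibiotics) that is Day 53, after both Day 33 and Day 42. For 5-day dosing, even Appendix A's earliest EOS, Day 39, is later than Day 33.

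**Illustration only.** The documents give no rate for such events. Assume 28 AP-SA02 subjects (two thirds of 42), onset uniform over 33 days, and a per-subject probability p of a similar, related, non-serious Grade 3 or higher event. The number of subjects affected is Binomial(28, p) for the criterion window and Binomial(28, p × 12/33) for the TEAE window. The last column is the second minus the third.

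| p | P(≥2 subjects by Day 33) | P(≥2 by Day 12) | P(≥2 by Day 33, but <2 shown as TEAEs) |
|---|---|---|---|
| 3% | 0.205 | 0.037 | 0.168 |
| 5% | 0.412 | 0.092 | 0.320 |
| 10% | 0.785 | 0.271 | 0.514 |

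If onset clusters near dosing, the last column shrinks.

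**The case against.** The two windows serve different purposes. The criterion prompts a case-level review that the DRC may hold on unblinded cases. It does not use the final SAP tables, and nothing requires a TEAE definition to match it. The affected set may also be small: an event must be non-serious, attributed to AP-SA02 and start after TOC, and to bear on the criterion it must be Grade 3 or higher. Many such events will be serious, because the protocol's fallback definition of Grade 3 includes hospitalization or its prolongation, which is also an SAE criterion. The 64% is a share of days, not of events. Late events of Grade 3 or higher still reach a table with an arm comparison. Pre-dose events dilute that table little, since screening lasts at most 3 days and those events cannot depend on treatment.

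All of this stands, and it limits the point. It does not supply the missing display: no summary gives, by arm, the drug-related events of Days 13 to 33, and a listing does not give rates.

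A reader might infer more than the documents support:
- **That every event meeting the criterion is missing from the drug-related tables.** Events with onset by Day 12 are TEAEs and appear there. SAEs are TEAEs through EOS.
- **That the Phase 1b primary endpoint is affected.** The Phase 1b windows coincide exactly.
- **That safety oversight is weakened or events are lost.** AEs are captured to EOS and listed, and the DRC's review does not rest on these tables.
- **That 30 of 42 days are uncovered under 14-day dosing (42 − 12).** This reads Day 12 literally and ignores the rule in both documents that moves TOC to 7 days after the last dose.
- **That delayed immune reactions are expected because antibodies are sampled to EOS.** The documents do not link that sampling to late AEs.

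**Conclusion.** The point holds as a reporting gap confined to Phase 2a. Non-serious study-drug-related AEs with onset after TOC and up to 28 days after last dose are not identified as drug-related in any planned summary table. The uncovered span is Days 13 to 33 with 5-day dosing, 21 of 33 days, and it is also 21 days if dosing is extended and TOC moves with it.

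This rests on reading the TEAE cut-off as the TOC visit and on the SAP 3.7.1 overview being the full set of categories. How many events fall in the gap cannot be known from the documents. The literal Day 12 in the definition is a wording weakness that matters only if dosing is extended. Closing the gap is a cheap improvement to the safety tables of a first-in-human trial; the existing TEAE analysis is not invalid without it.

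**What to change.** In SAP 3.7.1, for Phase 2a:
- Add overview rows and SOC/PT tables, by arm, of study-drug-related AEs, and of study-drug-related AEs of Grade 3 or higher, with onset after first dose through 28 days after last dose (or through EOS).
- Keep the existing through-TOC TEAE tables.
- Word the TEAE cut-off as the TOC visit for study drug, 7 days after the last dose, instead of a literal Day 12. Make the same edit in SAP 2.3.1 and 2.3.2, where the definition is repeated.
- Reconcile the TEAE window with the Protocol 4.3.2 window, or state in SAP section 6 why they differ and how the added tables cover the difference.

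The review criterion itself is not altered, and TEAE need not be redefined in either phase. The cost is SAP text, one onset-window flag and a few tables, settled before database lock. No new data are needed. The small downside is extra output with more background events, and the retained through-TOC tables keep these separable.

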9.2.1 Analysis of Phase 2a Endpoints

Phase 2a endpoints will be summarized descriptively for each treatment arm using appropriate proportions and means depending on the data type along with the 95% confidence interval. No formal hypothesis testing is planned.

Additional details will be described in the SAP.

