## 2.3 Study Endpoints

### 2.3.1 Phase 1b Multiple Ascending Dose Safety

The primary endpoint is safety. Safety will be evaluated by presenting summaries of the following:

- Treatment-emergent adverse events (TEAEs), which are defined as adverse events (AEs) occurring after the first dose of study drug through TOC for study drug (Day 12) or through EOS for serious AEs (SAEs);
- Vital signs; and
- Clinical laboratory evaluations.

The endpoints listed for Phase 2a may be assessed as secondary endpoints in the safety cohorts; however, these cohorts are exploratory and not powered for any efficacy variable.

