### 3.1.4 Hypothesis Testing

No formal testing will be done.

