### 3.7.2 Clinical Laboratory Tests

Blood samples for chemistry, hematology, coagulation, urinalysis, and serology testing will be obtained based on schedule of procedures ([Appendix A](#)). Descriptive statistics will be provided for chemistry, hematology, coagulation parameters using the International System of Units at baseline, each scheduled post-baseline visit, the minimum post-baseline value, the maximum post-baseline value, last post-baseline value and changes from baseline for each scheduled post-baseline visit, minimum, maximum, and last post-baseline values. Both scheduled and unscheduled post-baseline values will be considered for the summaries.

A paired t-test p-value will be used to compare the baseline value with each scheduled post-baseline values. An unpaired t-test p-value will be used for the change from baseline at each scheduled post-baseline visit to compare AP-SA02 and placebo.

All clinical laboratory data will be listed by subject based on randomized subjects. Laboratory values outside the normal ranges will be flagged in the data listings.

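### SAP 3.7 compares safety between arms only through chi-square and t-test p-values, without the 95% confidence intervals of protocol 9.2.1, and the chi-square is unreliable for sparse events at 28:14

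*SAP*

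**What the plan says.** Protocol 9.2.1 has the Phase 2a endpoints summarised descriptively for each arm, "along with the 95% confidence interval. No formal hypothesis testing is planned". The endpoint list in protocol 7.2 includes TEAEs, the proportion with AKI, vital signs and clinical laboratory evaluations. SAP 3.1.4 repeats the position: "No formal testing will be done".

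The SAP safety section does something different:

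- **Adverse events (3.7.1).** Eleven overview categories are tabulated, and "Counts and percentages of subjects will also be presented by SOC and PT for each of the categories in the overview". The next sentence adds: "Chi-square test p-value will be provided to compare AP-SA02 and placebo". The section does not say whether a continuity correction applies and names no exact test for sparse tables.
- **Laboratory values (3.7.2).** "An unpaired t-test p-value will be used for the change from baseline at each scheduled post-baseline visit to compare AP-SA02 and placebo". Section 3.7.3 does the same for vital signs.
- **AKI (3.7.5).** A proportion and a chi-square p-value.

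SAP 3.7 contains no confidence interval and no between-arm difference. Section 6 of the SAP lists six changes from the protocol, and this is not among them.

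**The concern.** There are two problems. First, the documents do not agree. The protocol promises intervals and no testing; the SAP safety section supplies tests and no intervals, while SAP 3.1.4 says there is no testing.

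Second, the named test suits these data poorly. The chi-square approximation needs reasonable expected counts, and most SOC and PT rows in a trial of 42 will not have them. With 2:1 allocation the failure is also uneven: a couple of events on placebo can fall below 0.05 while a larger number on AP-SA02 does not.

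Safety matters here. It is the stated purpose of Phase 1b ("The primary endpoint is safety") and part of the Phase 2a objective, in a first-in-human study. A p-value that is erratic for rare events, shown without an interval, does not tell the reader how large an excess remains possible.

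**Working it through.** **The plan's own figure.** The only power statement (SAP 2.2.4) concerns efficacy: at least 80% for 30% vs 80%, one-sided Fisher at 0.05, 38 MITT subjects. Exact enumeration at 25:13 gives 87.8%, so the statement holds as a lower bound. No corresponding figure is given for safety.

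**Inputs.** Phase 2a: 42 at 2:1, so 28:14. Phase 1b: two cohorts of four at 3:1, so 6:2 pooled. SAP 3.7 compares each phase with its own placebo. Assumptions: two-sided 0.05 (the SAP sets no safety level), the uncorrected Pearson statistic, and all randomised subjects dosed.

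**Expected counts.** With t events in total, the expected number on placebo is t × 14/42 = t/3. A value of 5 needs t = 15 of 42 subjects.

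**Single tables at 28:14.** For a/28 vs b/14, with t = a + b:

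X² = 42 × [a(14 − b) − b(28 − a)]² / [28 × 14 × t × (42 − t)]

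- 0/28 vs 2/14: 42 × 56² / (28 × 14 × 2 × 40) = 4.20, p = 0.040. The expected event counts are only 1.33 and 0.67. Fisher: C(14,2)/C(42,2) = 91/861 = 0.106. Yates: 0.200.
- 6/28 vs 0/14: 42 × 84² / (28 × 14 × 6 × 36) = 3.50, p = 0.061. Fisher: 0.083.
- 7/28 vs 0/14: p = 0.040. With one placebo event, 9/28 gives p = 0.073 and 10/28 gives p = 0.047.

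**Rejection rates at 28:14.** Every table is weighted by its binomial probabilities and counted when Pearson p < 0.05.

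| True rate, AP-SA02 vs placebo | Flags AP-SA02 excess | Flags placebo excess |
|---|---|---|
| 20% vs 5% | 17% | 0.04% |
| 30% vs 10% | 30% | 0.02% |
| 30% vs 0% | 78% | 0 |
| 5% vs 5% | 0.02% | 3.8% |
| 10% vs 10% | 0.4% | 3.2% |
| 20% vs 20% | 2.1% | 2.6% |

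For 20% vs 5%, detection falls to 9.4% with Fisher and 4.6% with Yates.

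**Phase 1b at 6:2.** 4/6 vs 0/2 gives p = 0.102 and 5/6 vs 0/2 gives p = 0.035. In the other direction, 0/6 vs 1/2 gives p = 0.064.

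**t-tests.** 80% power needs a true difference of 0.94 SD at 28:14 or 2.75 SD at 6:2.

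**What an interval would show.** The Newcombe limits are d − √[(p₁ − l₁)² + (u₂ − p₂)²] and d + √[(u₁ − p₁)² + (p₂ − l₂)²], where l and u are Wilson limits. For 6/28 the Wilson limits are 0.102 and 0.395; for 0/14 they are 0 and 0.215. With d = 0.214:

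- lower: 0.214 − √(0.112² + 0.215²) = −0.03
- upper: 0.214 + √(0.181² + 0²) = 0.40

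The result is +21 points, 95% CI −3 to +40.

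**The case against.** A fair defence is that these p-values are incidental. The tables show counts and percentages, so 6/28 vs 0/14 appears as 21% vs 0%. The SAP sets no safety significance level or decision rule. Low power comes from the sample size rather than the choice of test, and an interval for 6/28 vs 0/14 also includes zero. Protocol 9.2.2, the safety section, promises no interval. The clash between p-values and no formal testing runs through the efficacy sections as well. Much of this stands, and it rules out several stronger readings that a reader might infer:

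- **That safety is judged only by p-values.** It is not. Besides the counts, SAP 3.7.1 provides that "Listings will be presented specifically for SAEs and TEAEs leading to discontinuation of study drug based on randomized subjects". Abnormal vital signs and QTcF categories are counted without p-values. During the trial the DRC works from event-count triggers (protocol 4.3.2).
- **That the test cannot flag a large excess on AP-SA02.** It can: 7/28 vs 0/14 and 5/6 vs 0/2 reach p < 0.05, and 30% vs 0% has 78% power at 28:14.
- **That a trivial placebo excess is flagged in both phases.** At 6:2 one placebo event against none is not flagged (p = 0.064). At 28:14 the flag on two placebo events depends on the uncorrected statistic, which the SAP does not specify.
- **That a non-significant result will be taken as reassurance.** The documents contain no such rule.
- **That the protocol promises risk differences.** It promises per-arm intervals, for Phase 2a only.

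The defence does not explain why SAP 3.7 omits intervals for safety items on the Phase 2a endpoint list, or why Section 6 is silent. Nor does it justify a chi-square on tables with expected counts near one. Fisher or Yates removes the flag on 0/28 vs 2/14 but lowers detection of harm further, so changing the test alone would not make the p-values informative.

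**Conclusion.** The point holds as a reporting and consistency defect. SAP 3.7 replaces the protocol's per-arm 95% intervals with between-arm p-values, contrary to protocol 9.2.1 and its own section 3.1.4, and does not declare the change. For rare events at 28:14 the uncorrected chi-square is unreliable. It can call two placebo events significant, it has about 17% power for 20% vs 5%, and at a common 5% rate its false flags fall almost entirely on a placebo excess (3.8% vs 0.02%). At a 20% rate the imbalance is small (2.6% vs 2.1%), so it concerns sparse SOC and PT terms rather than common overview rows.

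The figures rest on two-sided 0.05, no continuity correction, and the planned 28:14 with everyone dosed. The documents do not show that any safety decision depends on these p-values. The change should be made before the SAP is final, but it does not threaten the conduct of the trial.

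**What to change.** In SAP 3.7.1 to 3.7.3 and 3.7.5:

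1. Add the per-arm 95% confidence intervals of protocol 9.2.1 for the Phase 2a safety endpoints.
2. Replace the between-arm p-values with estimates. Use a risk difference with a Newcombe or exact 95% interval for the overview AE categories, SAEs, Grade 3 or higher TEAEs and AKI, and a mean difference with a 95% interval for laboratory and vital-sign changes. These between-arm intervals add to what the protocol promises.
3. If p-values are kept, use Fisher's exact test for proportions, label all of them descriptive, and list the departure from protocol 9.2.1 in SAP Section 6.

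The cost is SAP text and a small change to table shells. The intervals will be wide and power will not rise; the gain is that readers see what the trial cannot exclude.
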